COVER PAGE FOR PROTOCOL AND STATISTICAL ANALYSIS PLAN

Official Study Title: Improving Retention of Nasoenteric Feeding Tubes in Pediatric Patients Using a Nasal Bridle

NCT number: NCT 04621734

IRB Approval Date: 04/09/2020

Unique Protocol ID: HSC20190225H

Form CT

UTHSA Clinical Trial Description

This form is not mandatory. Other documents are acceptable if equivalent information is provided.

UTHSCSA Tracking Number (internal use only)	HSC20190225H	1. Original Version Date	07/01/2019
		1.1. Revision Date(s) add rows as needed	10/08/19, 04/09/2020

2. Background

Briefly discuss the important literature relevant to the trial and that provides background for the trial. Include the importance of the trial and any relevant treatment issues or controversies.

Nasoenteric feeding tubes are commonly used in the Pediatric ICU as a way to enterally provide nutrition and medication. The traditional method of securing these tubes has been by the use of adhesive tape on the face but unintentional tube dislodgment continues to be a common occurrence. Tube dislodgment leads to delays in nutrition and medication administration, multiple tube replacements, which result in discomfort and extra radiation exposure, and increased consumption of hospital resources with the additional cost of replacement tubes and radiographs. The nasal bridle (BridlePro) is an FDA approved device invented and manufactured by Applied Medical Technology, Inc (AMT) and is an alternative securement method using the structure of the nasal cavity to secure the nasoenteric tube in both adults and children. There have been several studies in the adult population revealing a reduction in dislodgment but only 1 pediatric study, published in 2016, in a very narrow population. This is an investigator-initiated study to compare tube dislodgment rates when the tube is secured with adhesive tape vs the AMT BridlePro device.

3. Objectives and Endpoints *All data points collected in the study should support an objective or have a regulatory purpose.*

Complete the table – add rows as needed.

3.1. Objective(s) Clearly and concisely define the primary and secondary outcomes.	3.2. Endpoint Clearly define the endpoints. (endpoints are the basis for concluding that the objective has been met).	3.3. Justification for Endpoint Briefly explain why the endpoint(s) were chosen.
Primary outcome: Tube dislodgment rate Secondary outcomes: Time to tube dislodgment, cost of additional feeding tubes and radiographs, number of additional radiographs needed for tube replacement, time of missed nutrition	The endpoint will be when a patient no longer requires a nasoenteric tube because full oral feedings have been met, when a tube is dislodged and successfully replaced, or when the bridle has been in place for 30 days.	When a patient no longer requires a feeding tube, it is standard practice to remove the tube. When a tube is dislodged, the data will be collected for the study and they will have fulfilled the objective and the patient will resume standard treatment. The BridlePro is FDA approved for 30 days of use.

4. Rationale

Briefly state the reason for conducting the clinical trial.

The reason for conducting the investigator initiated clinical trial is to compare the use of a nasal bridle to adhesive tape as a way to secure nasoenteric feeding tubes to improve retention rates.

5. Study Design

5.1. Number of Groups/Arms 2 Group name(s) Control arm and study arm			
5.2. Overall Design Select all applicable			
	Randomization		Cluster Randomized
	Group-Sequential		Adaptive Design

	Parallel Design				Placebo-Controlled							
	Superiority				Equivalence					Non-inferiority		
Device			Pilot			Pivotal				Post-Approval		
Drug/Biologic		Phase 1		Phase 1/2		Phase 2		Phase 2/3		Phase 3		Phase 4
 Dose escalation		If yes, details →										
 Dose ranging		If yes, details →										
 Sub-studies		If yes, details →										
5.3. Other Design Details:												

6. Study Population												
6.1. Study Population(s) Label/Name To add more populations – select a row, copy & paste			6.2. Identify the criteria for inclusion The criteria that every potential participant must satisfy, to qualify for study entry. All individuals in this study population must meet all of the inclusion criteria in order to be eligible to participate in the study				6.3. Identify the criteria for exclusion The characteristics that make an individual ineligible for study participation. All individuals in this study population meeting any of the exclusion criteria at baseline will be excluded from study participation.					
Patients who require a nasoenteric feeding tube, admitted at University Hospital, ages 0-18 yo			Need for nasoenteric feeding tube Admitted at University Hospital Age 0-18 yo				Facial trauma, nasal airway obstructions, thrombocytopenia (<100 K/µL), s/p septoplasty, patients with vomer bone graft, nasoenteric feeding tube placed and secured prior to being screened for study, contraindication for the use of the BRIDLEPro Does not meet inclusion criteria					
6.4. Will screen failures be allowed to re-screen at a later date?				No		Yes	If yes, describe criteria below ↓					

7. Study Intervention(s) being tested or evaluated												
This can include prevention, diagnostic or therapeutic interventions (e.g., drug or device) or educational, health services or basic science interventions (e.g., educational program, health care delivery model, or examining basic physiology)												
Dislodgment rates of nasoenteric feeding tubes when secured with the AMT BridlePro compared to adhesive tape. The adhesive tape will be the tape available in the unit and will be placed by the nurse or provider at the time of nasoenteric tube placement. The tape will be placed around the tube and secured to the cheek on the side of tube. The tape will be replaced as needed per nursing discretion when soiled or the adhesive properties are failing and this information will be tracked. The AMT BridlePro will be placed by the nurse or provider at the time of nasoenteric tube placement. Placement will use the BridlePro system included in the individual BridlePro packaging. Placement and securement will follow manufacturer recommendations and teaching. The BridlePro encircles the vomer bone of the nasal cavity to secure the tube. Sedation medication may be given per standard of care for nasoenteric tube placement at the discretion of the provider team but no separate or additional sedation medication will be given for securement with adhesive tape or the BridlePro.												

8. Protocol-Directed procedures, items, services or tests												
List all procedures directed by the study plan - including items or services provided as part of routine or conventional care and those needed to diagnosis or treat research related complications.												
Important Note – The protocol directed procedures listed must match those in the Schedule of Activities (attachment)												
8.1. Drugs (trade and generic, dosage, route of administration)												
N/A												

8.2. Devices

Nasoenteric feeding tube will be placed by the bedside nurse as part of routine care. AMT BridlePro will be placed by trained nurses for patients on the study arm of the trial.

8.3. Biologics

N/A

8.4. Laboratory Tests

N/A

8.5. Imaging Procedures

No additional imaging will occur as part of the study. However, confirmatory radiograph for proper placement of the initial nasoenteric tube as part of our current standard of care will continue. Additional confirmatory radiographs for proper placement of replacement nasoenteric tubes as part of routine care when a tube is dislodged will also continue.

8.6. Other Research Procedures (e.g., other safety and efficacy assessments.)

Chart review/Data collection

8.7 Attach a Schedule of Activities (SOA) [Excel File](#) [Download the Template here: [Schedule of Activities](#)]

Check to indicate that the SOA Excel File is attached →

9. Preparation/Handling/ Storage/Accountability of Investigational Drug, Biologic, or Device

- N/A - This study does not include any investigational products (e.g. drugs, devices or biologics)
- N/A - An Investigator Brochure is attached
- N/A - A Drug/Device Manual is attached

9.1. Acquisition and accountability

State how the study intervention and control product will be provided to the investigator. Describe plans about how and by whom the study intervention will be distributed, including participation of a drug repository or pharmacy, and plans for disposal of expired or return of unused product.

AMT representative will provide in-person training for the nurses and providers placing the BridlePro and will provide the nasal bridles as per the clinical trial material transfer agreement. The nasoenteric tubes that will be used in the control and study arm are the standard tubes used in the unit and adhesive tape that is used for securing tubes in the control group.

9.2. Formulation, Appearance, Packaging, and Labeling

Describe the formulation, appearance, packaging, and labeling of the study intervention and control product, as supplied. Information in this section can usually be obtained from the IB or the package insert, or device labeling. This section should include the name of the manufacturer of the study intervention and control product.

AMT manufactures and provides the study intervention product. The BridlePro will be labeled as part of standard device labeling indicating the appropriate sized bridle based on the nasoenteric tube used.

9.3. Product Storage and Stability

Describe storage and stability requirements (e.g., protection from light, temperature, humidity) for the study intervention and control product. For studies in which multi-dose vials are utilized, provide additional information regarding stability and expiration time after initial use (e.g., the seal is broken).

The nasogastric tubes and nasal bridles will be stored in the supply room in each unit (7th Floor Sky Tower and PCCU).

9.4. Preparation

Describe the preparation of the study intervention and control product, including any preparation required by study staff and/or study participants. Include thawing, diluting, mixing, and reconstitution/preparation instructions in this section. For devices, include any relevant assembly or use instructions.

Device assembly of the BridlePro system per package instructions and training provided by AMT representative.

10. Study Intervention Additional Details**10.1. Measures to Minimize Bias: Randomization and Blinding**

This section should contain a description of randomization and blinding procedures (if applicable to the study design). It should include a description or a table that describes how study participants will be assigned to study groups, without being so specific that blinding or randomization might be compromised. Plans for the maintenance of trial randomization codes and appropriate blinding for the study should be discussed. The timing and procedures for planned and unplanned breaking of randomization codes should be included. Include a statement regarding when unblinding may occur and who may unblind. Provide the criteria for breaking the study blind or participant code. Discuss the circumstances in which the blind would be broken for an individual or for all participants (e.g., for serious adverse events (SAEs)). Indicate to whom the intentional and unintentional breaking of the blind should be reported.

Study participants will be randomized to the control or study arm using REDCap Randomization Module. Sealed envelopes will be locked in the PICU/PCCU where nasogastric tubes and bridles will be stored. When a patient meets criteria for the study, the study administrator will be notified, an envelope will be drawn to randomize the participant into one of the two groups and patient

information will be recorded in a log stored on a password protected UH computer share drive.

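### Section 10.1 draws the envelope without confirming that a bridle can be placed at that insertion, and 12.3 as worded would then count a taped bridle-arm child as a control

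*Combined protocol and SAP*

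**What the plan says.** Section 10.1 gives the trigger for randomisation: "When a patient meets criteria for the study, the study administrator will be notified, an envelope will be drawn to randomize the participant". The criteria it refers to are in 6.2 and 6.3. They cover need for a tube, age, being "admitted at University Hospital", and exclusions that concern the child, including a contraindication to the bridle. None concerns staff or stock.

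Other sections state what the bridle needs:

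- **Placer.** Section 8.2: "AMT BridlePro will be placed by trained nurses for patients on the study arm of the trial". Section 7 words it differently: "The AMT BridlePro will be placed by the nurse or provider at the time of nasoenteric tube placement".
- **Moment.** The same sentence of section 7 ties the bridle to tube insertion, and 6.3 excludes a child whose tube is already in and secured at screening.
- **Size.** Section 9.2 has the label "indicating the appropriate sized bridle based on the nasoenteric tube used".
- **Stock.** Section 9.3: "The nasogastric tubes and nasal bridles will be stored in the supply room in each unit (7th Floor Sky Tower and PCCU".

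Tape is whatever the unit already has (section 7). The plan does make some provision for delivery. Section 9.1 plans in-person training for nurses and providers, and 10.1 says "Sealed envelopes will be locked in the PICU/PCCU where nasogastric tubes and bridles will be stored".

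Section 12.3 describes the two analysis groups by the securement that was used. No section says what happens to a child who draws the bridle and does not receive it. Section 6.4 rules out re-screening of screen failures.

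**The concern.** The draw depends on the child alone, while delivery of one of the two arms also depends on who is present and what is in the supply room. A child can therefore draw the bridle at an insertion where only tape can be applied. For these logistic reasons the failure falls essentially on the bridle arm.

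What follows depends on how such a child is analysed. If the child is grouped by the securement received, the groups are no longer those that randomisation formed. If non-placement is related to unit, shift, age or tube size, it brings selection with it. If the child is kept in the arm drawn, the comparison stays randomised but the difference shrinks. With 30 per arm there is little room for either, and the first cannot be reliably repaired afterwards.

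**Working it through.** **1. Conditions for the draw against conditions for delivery**

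| Condition | Source | Confirmed before the draw? | Needed for tape? |
|---|---|---|---|
| No clinical contraindication to the bridle | 6.3 | Yes | No |
| Trained placer at this insertion | 8.2, 9.1 | No | No |
| Bridle that fits the tube | 9.2 | No | No |
| Bridle stock on the unit | 9.3 | Not required, but envelopes are kept with the stock (10.1) | No |

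Two conditions, placer and size, have no confirmation step at all.

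**2. The plan's own figure**

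Section 12.2 gives 30 per arm with no test, alpha, power or dislodgment rates, so it cannot be reproduced. Back-solving under assumptions (two-sided 0.05, 80% power, no continuity correction), 30 per arm suffices if the bridle risk is at most 9.4% against 40% on tape, or at most 16.5% against 50%. All risks and all non-delivery shares below are likewise assumptions.

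**3. Grouping by securement used, as 12.3 is worded**

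Take 3 of 30 bridle children taped instead.

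- *Power, if non-placement is unrelated to risk* (40% v 10%, normal approximation): 78.0% with full delivery; 76.8% if the 3 move to tape (33 v 27); 75.2% if they are dropped (30 v 27). The loss is small.
- *Bias, if it is related to risk.* Suppose the bridle has no effect and 12 of 30 (40%) dislodge in each arm.
  - If all 3 taped children dislodge, the groups become tape (12+3)/33 = 45.5% and bridle (12−3)/27 = 33.3%, a spurious 12.1-point benefit.
  - If none of the 3 dislodges, they become 12/33 = 36.4% and 12/27 = 44.4%, a spurious 8.1-point harm.
  - If the 3 are dropped instead, tape stays at 40% and bridle is 33.3% or 44.4%, an error of +6.7 or −4.4 points.

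These are extremes for 3 children, not expected values.

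**4. Grouping by arm drawn**

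With undelivered share f, and undelivered children at the tape risk, bridle-arm risk = (1−f)·p_bridle + f·p_tape, so the difference shrinks by the factor (1−f). For 40% v 10% at f = 10%: 0.9×0.10 + 0.1×0.40 = 0.13, and the difference goes from 30 to 27 points.

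Power of the two-sided exact Fisher test at 0.05, n = 30 per arm, all outcomes enumerated:

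| Tape v bridle | f = 0 | 5% | 10% | 20% |
|---|---|---|---|---|
| 40% v 10% | 0.705 | 0.640 | 0.575 | 0.447 |
| 50% v 15% | 0.777 | 0.717 | 0.653 | 0.521 |
| 40% v 15% | 0.489 | 0.437 | 0.388 | 0.298 |

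At f = 10% the loss in these rows is 0.130, 0.124 and 0.101. At f = 0 there is none.

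**The case against.** The plan is not careless about delivery. It trains nurses and providers, stocks bridles on the units and keeps the envelopes with that stock, and the study administrator is notified before the draw. Nothing shows that the trained nurse and the bedside nurse are different people, and the sizing text in 9.2 is a labelling statement that does not suggest any size would be out of stock. The non-delivery share is not in the documents and could be zero. All of this stands. It lowers the probability and limits how strongly the point can be put, but it puts no confirmation step before the draw.

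A reader might infer that the trial as planned will be diluted and that the power losses in step 4 describe it. The documents do not support that. As 12.3 is worded, a taped child is not kept in the bridle group, and power then barely moves (step 3). The dilution figures apply only to a comparison by arm drawn, at an assumed share.

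A reader might also infer that a check before the draw would abolish the problem. It would not: a placement can still fail after the draw with a trained placer and a matching bridle present. Nor does the hospital-wide wording of 6.2 show that children will be enrolled where no bridles are held, since the envelopes are kept with the stock.

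**Conclusion.** The point holds as a limited one that should be acted on. The draw rule in 10.1 allows a bridle to be allocated at an insertion where it cannot be placed, and no section rules this out. The consequence that follows from the plan's wording is loss of the randomised comparison through 12.3. In the constructed example of 3 taped children and no true effect, the error can range from 12.1 points in favour of the bridle to 8.1 points against it. Under analysis by arm drawn the consequence would instead be lost power: 0.71 to 0.58 at assumed risks of 40% v 10% and 10% undelivered.

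Both sizes rest on assumed risks and an assumed share, and both vanish if every bridle is delivered. Confidence is therefore moderate. The case for acting rests on the low cost of a better rule, not on evidence that delivery will often fail.

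**What to change.** - **10.1:** draw the envelope only after the study administrator has recorded that a trained placer and a bridle matching the tube are available for this insertion. Because the record precedes allocation, children passed over at this step introduce no between-arm bias.
- **12.3:** compare children by the arm drawn, and record any child who does not receive the allocated securement, with the reason. Remaining non-placement then does not move children between groups.
- **6.4:** state that a child not randomised for this logistic reason is not a screen failure and may be considered at a later insertion. Otherwise the bar on re-screening could lose such children for good.
- **7 and 8.2:** reconcile the two statements of who places the bridle, so that the availability record has a clear meaning.
- **6.2:** leave unchanged.

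The cost is a few sentences and a small addition to the log, which may have to be opened before the draw since 10.1 describes it only alongside randomisation. Accrual should be slightly slower; the documents give no accrual figures to quantify this. The check reduces non-delivery but does not eliminate it, and comparison by arm drawn accepts some dilution from what remains.

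### Section 12.3 forms the analysis groups by the securement used, not by the arm assigned, so children can leave one arm after the allocation is known

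*Combined protocol and SAP*

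**What the plan says.** **Analysis groups.** Section 12.3, under a prompt asking which participants enter each analysis dataset, describes the study group as children whose tube was secured with the bridle and the control group as children whose tube was secured with tape. It does not refer to the arm assigned. Section 12.4 lists endpoints and adds no rule on populations.

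**Allocation.** Section 10.1 states: "Study participants will be randomized to the control or study arm using REDCap Randomization Module". It continues: "Sealed envelopes will be locked in the PICU/PCCU where nasogastric tubes and bridles will be stored". Then: "When a patient meets criteria for the study, the study administrator will be notified", and "an envelope will be drawn to randomize the participant into one of the two groups". The record it names comes last in the account: patient "information will be recorded in a log stored on a password protected UH computer share drive". How the REDCap module and the envelopes relate is not stated. Nor is any entry of eligibility before the draw.

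**Eligibility and placement.** Section 6.3 says that children meeting any "of the exclusion criteria at baseline will be excluded from study participation", and one such criterion is a "contraindication for the use of the BRIDLEPro". Section 6.4 does not allow re-screening. Section 7 says: "The AMT BridlePro will be placed by the nurse or provider at the time of nasoenteric tube placement".

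**The concern.** Randomization protects the comparison only if children are compared in the groups to which chance assigned them. Three features of this plan, taken together, put that at risk.

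- Tape on the cheek and a bridle around the vomer bone cannot be mistaken for each other, and no blinding is described. Everyone at the bedside knows the arm.
- A contraindication to the bridle is a judgement about one arm's device. The bridle goes in with the tube, so anything noticed at insertion is noticed with the arm already known.
- Section 12.3 groups by what was used. A child drawn to the bridle and then judged unsuitable would, as worded, drop out of the bridle group or move to the tape group. A contraindication to the bridle gives no matching reason to leave the tape arm.

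If such children differ in their risk of dislodgment, the primary comparison is biased. With no stated record of eligibility before the draw, the analysis might not show that it had happened.

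**Working it through.** **Inputs from the documents.** 30 children per arm (section 12.2), so 60 in total. The documents give no dislodgment rate, effect size, significance level or expected number of children not receiving their assigned securement, so there is no planned figure to reproduce.

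**Assumptions, for scale only.** No true difference between arms. 24 of the 60 children are at higher risk, so each arm holds 12 of 30 on average. Risk of dislodgment in the higher-/lower-risk children is 45/30, 60/25 or 70/15%, so the gap D is 15, 35 or 55 points. A few children drawn to the bridle are not bridled.

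**Formula.** With no true effect, the expected apparent advantage of the bridle (tape rate minus bridle rate) is

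D × (higher-risk share of the tape group − higher-risk share of the bridle group).

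| Handling of the children not bridled | Difference in shares | D = 15 | D = 35 | D = 55 |
|---|---|---|---|---|
| Analysed as assigned | 12/30 − 12/30 = 0 | 0.0 | 0.0 | 0.0 |
| 1 higher-risk, dropped | 12/30 − 11/29 = 0.0207 | 0.3 | 0.7 | 1.1 |
| 1 higher-risk, counted with tape | 13/31 − 11/29 = 0.0400 | 0.6 | 1.4 | 2.2 |
| 3 higher-risk, dropped | 12/30 − 9/27 = 0.0667 | 1.0 | 2.3 | 3.7 |
| 3 higher-risk, counted with tape | 15/33 − 9/27 = 0.1212 | 1.8 | 4.2 | 6.7 |
| 3 unrelated to risk, dropped | 12/30 − 10.8/27 = 0 | 0.0 | 0.0 | 0.0 |
| 3 lower-risk, dropped | 12/30 − 12/27 = −0.0444 | −0.7 | −1.6 | −2.4 |

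Shifts are in percentage points.

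**Check by simulation.** With 400,000 trials per scenario, 3 higher-risk children dropped gave shifts of 1.00, 2.34 and 3.71 points; counted with tape, 1.80, 4.25 and 6.67. These agree with the formula within simulation error.

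**False positives.** The same simulation counted significant results favouring the bridle (uncorrected chi-square, two-sided 5%):

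- analysed as assigned: 2.3 to 2.4%;
- 3 dropped: 3.0, 3.9 and 4.9%;
- 3 counted with tape: 3.6, 5.3 and 8.0%.

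**What the calculation isolates.** The method of allocation does not enter it. All of the computed bias comes from how 12.3 forms the groups, and all of it disappears when the same children stay in their assigned arm.

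**The case against.** **Section 12.3 may be only a label.** It may simply name the two arms by their treatment. Section 8.2 speaks of bridles for patients on the study arm, section 12.2 counts patients by arm, and 12.3 states no rule for excluding or moving anyone. This is fair: a planned as-treated analysis is not proved. But 12.3 is where the plan says who is analysed where, and the only criterion it gives is the securement used. An analyst who followed it literally would regroup children.

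**The scenarios are chosen.** Nothing in the documents links unsuitability for the bridle to dislodgment risk. Three higher-risk children are a quarter of the 12 expected in the arm. This stands: the figures show what could happen, not what is expected.

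**Recording eligibility first does not stop a late judgement.** The arm is still known at insertion. This also stands: the gain is that a late judgement can be traced.

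**Stronger readings a reader might infer.** One is that the envelopes break concealment, or that staff could steer children between arms. The documents do not support this. The envelopes are sealed and locked, the criteria are met and the administrator is notified before the draw, exclusions apply at baseline, and steering would need advance knowledge of the next allocation. Another is that REDCap and the envelopes contradict each other. REDCap may generate the list and the envelopes carry it; the text is incomplete on this, not inconsistent. Finally, the separate Schedule of Activities is not part of the supplied text, so an eligibility record may exist elsewhere.

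**Conclusion.** The point holds as a defect in the wording of 12.3. It allows one-sided loss or movement of children after an openly known assignment, when a rule that removes the problem costs one sentence.

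Under the assumed rates with no true effect, 3 affected higher-risk children favour the bridle by 1.0 to 3.7 points if dropped and by 1.8 to 6.7 points if counted with tape; one child gives 0.3 to 2.2 points. The direction depends on who the children are. The documents do not show that any child will be affected, or how many.

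The order of steps in 10.1 is sound. The missing eligibility record is a smaller matter of traceability, and its benefit is not quantified.

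**What to change.** **Main change, section 12.3.** Add: *Children are analysed in the arm assigned at randomization, whatever securement was used; any child found unsuitable for the bridle after assignment stays in that arm for analysis and is counted and reported by arm.* This governs the analysis only; it does not say how such a child's tube should be secured. The cost is one sentence. If the bridle does work, unbridled children in its arm dilute the estimate somewhat: with 3 of 30, one tenth of the arm would not have had the device.

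**Supporting change, section 10.1.** REDCap is already named for randomization (10.1) and data collection (10.2). State that the module releases the arm only after all eligibility items, including absence of a bridle contraindication, have been entered. If a login at allocation is impractical, keep the envelopes, but state that they carry the REDCap list, are numbered in sequence, and are opened in order only after the child's eligibility is logged with date and time. The cost is a login or a timed log entry for each child.
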